8.2 Screening and Eligibility Assessment

Children who clinically warrant an asthma review, which are also our potential participants, will be identified by the direct care team from participating GP sites. The direct care team will search their practice electronic database for children who meet the inclusion criteria using age limits "5 to 16 years," and to include children who are either on the asthma register or based on asthma medications prescribed as detailed in the inclusion criteria above.

Once identified, the direct care team will send by post the standardised PIS along with the asthma review invitation letters to families. The invitation letter will invite families to phone the GP practice to book onto an asthma review clinic. We anticipate that there will be a minimum of 1 week between the time families receive PIS and the next available asthma review clinic.

Demographics

The date of birth, gender, race, primary language and country of birth will be recorded by the research team in the CRF following written consent at the asthma review.

Medical History

Details of length of asthma diagnosis or duration of “asthma” symptoms will be recorded at time of asthma review by study team following written consent along with concomitant medication and any physical examination (detailed below).

Concomitant Medication

All prescription “asthma” medications (bronchodilators, inhaled steroids, leukotriene receptor antagonists etc.) will be recorded on CRFs and assigned to a corresponding asthma treatment step as detailed in BTS/SIGN asthma guidelines. We will also record number of days of oral steroids prescribed in the preceding 6 months.

Physical Examination

Height and weight of participating children will be recorded.

8.3 Baseline Assessments

Health Care Workers’ Training Needs

The study team will gather information using site survey and readiness for change questionnaires at each participating practice. It is expected that practice GPs, nurses, HCAs and managers will complete these questionnaires.

The study team will seek the views particularly, but not exclusively, of the healthcare workers performing the objective tests (spirometry and FeNO) on the delivery and content of the training package and the training time available to those performing the tests.

Assessments Performed as Part of Recommended Standard Asthma Review

Asthma control test: We will use validated asthma control tests for children 4 to 11 years (7 questions) (17) and children 12 years and older (5 questions).

Check inhaler technique: Inhaler technique will be checked by the PN/HCA following training if required. An instruction sheet with written information and pictures will be given to the family.

Check prescription record: We will check and document the electronic prescribing record and dispensing record where available for asthma medication in the previous 6 months including the number of reliever and preventer inhalers. As part of the asthma review the practice PN/HCA will also check the prescription records and inform the GP if they have concerns regarding: suboptimal asthma control; where reliever and preventer medication use are unbalanced for example in cases where preventer prescribing is low and reliever prescriptions are high; and where there are concerns regarding adherence (i.e. fewer than expected number of inhalers dispensed).

Any child presenting to the review visit unwell or with poor lung function (FEV1 <75% predicted) will be referred to the practice GP for assessment.

Written personalised asthma action plan: All children will be given a written personalised asthma action plan. Where children already have an action plan this will be reviewed.

Spirometry and FeNO testing: Children will be asked to perform spirometry and a FeNO measurement where indicated.

Incentive spirometry: Forced expiratory manoeuvres will be performed according to American Thoracic Society/European Respiratory Society standards (15,16). Children will be invited to perform a forced expiratory manoeuvre at least three times with a maximum of eight attempts. Where readings are within 5% of each other the recorded value is the best of these three readings. Achieving such reproducibility can be difficult in younger children and we will then use the best effort as the recorded values. Incentive spirometry will be used in all children, whereby visual aids are provided on the spirometer screen like for example a series of candles have to be blown out encouraging the child to breathe out hard for longer. This technique is very successful, even in young children. The PN/HCA will assess the forced expiratory volume in 1 second (FEV1) and the FEV1/FVC ratio. Where the FEV1/FVC ratio is lower than the GLI threshold or where FEV1 is <80% predicted they will perform reversibility testing using Salbutamol 400 micrograms (4 puffs) given via spacer and repeat the forced expiratory manoeuvre after 15 minutes. Any change in FEV1 of $\geq 12\%$ will be taken as demonstrating reversible airway narrowing and this in conjunction with the clinical history will be taken as diagnostic for the presence of asthma. The data and the lung function trace will be recorded on the practice electronic patient records and the GP informed.

FeNO measurements: Will be taken in all children five years and older using a NIOX MINO (Aerocrine, Sweden), which is a hand-held device with a mouthpiece. The result of the FeNO concentration in exhaled breath is available immediately in parts per billion (ppb) and we will use the cut-off value of 35ppb and above as diagnostic for asthma as per NICE guideline.

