Proposed NICE asthma diagnostic algorithm: For children aged 5 to 16 years and adults with symptoms of asthma the draft guideline recommends spirometry testing for diagnosis and where obstructive spirometry is present bronchodilator reversibility should be considered. FeNO, an inflammatory marker in exhaled breath linked with asthma, should be considered where spirometry is normal and where obstructive spirometry does not reverse with bronchodilators. The proposed NICE guidance for diagnosis of asthma is summarised below.

[figure not shown]
Diagnostic criteria for asthma in children aged 5-16 years:

- Clinical symptoms compatible with the diagnosis

- Objective tests including
 - Obstructive spirometry
 - Reversibility following short acting beta-2-agonists ($\geq 12\%$ increase in FEV₁)
 - Raised FeNO (≥ 35 ppb)
 - Peak flow variability ($>20\%$)

No single positive test is diagnostic for asthma

Draft NICE diagnostic algorithm for children aged 5-16 years with suspected asthma

Asthma monitoring: Spirometry should be done in adults with asthma and considered in children at every asthma review.

Spirometry: Spirometry is available in primary care and performed in adults with COPD where it is already part of the Quality Outcome Framework (QOF). NICE and BTS/SIGN state that spirometry is preferable to measurement of peak expiratory flow because it allows clearer identification of airflow obstruction, and the results are less dependent on effort.

Spirometry is however only rarely performed in children in primary care. Children benefit from visual incentive spirometry which requires a special spirometer usually not available in GP

practices. Interpretation of spirometry in children also requires a slightly different approach. Consequently, practice nurses/health care assistants (PN/HCA) usually have no experience in performing and interpreting spirometry in children, but could be trained to do so. The amount of training required and how best to deliver it are currently not known and addressing these knowledge gaps is one of the main implementation research questions.

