5.2 Secondary Objectives

The secondary objectives relate to investigating the impact of implementing the new NICE guidelines on the processes and outcomes of childhood asthma care and will include:

1. The number of children in which a diagnosis of asthma can be confirmed using spirometry and FeNO testing
2. The number of misdiagnoses identified using lung function tests
3. The impact of implementation to health economics

[figure not shown]

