We will assess additional capacity needs by timing how long each lung function test takes to perform in addition to the routine asthma review at each surgery. We will also be able to evaluate the number of patients who can be reliably reviewed and tested per session, thus elucidating how many sessions a typical GP practice would have to support in order to provide regular lung function testing to children. This information would further inform the costs required to sustain new NICE recommended practice.

Health Economic Analysis

This will take the form of a questionnaire delivered to parents at the time of the asthma review and a further postal questionnaire 3-6 months following the review. Analysis of this data will be supported by a health economist.

Assessment of Impact of Implementation to Processes of Care

Following the initial review appointment, we will access the electronic records of consented participants. We will seek information on changes to prescribed asthma medications (bronchodilators, oral steroids and inhaled steroids), exacerbations since review, hospital admissions/attendances since review and whether their originally diagnoses had changed as a result of the availability of objective tests.

With parental consent, we will also send out a repeat ACT by post 3-6 months following the initial review.

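### Sections 4 and 8.3 disagree on when reversibility is tested and what confirms asthma, so the guideline-labelled count of confirmed cases depends on an undefined term, 'obstructive spirometry'

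*Combined protocol and SAP*

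**What the plan says.** Section 8.3 (Incentive spirometry) sets the study's trigger: "Where the FEV1/FVC ratio is lower than the GLI threshold or where FEV1 is <80% predicted they will perform reversibility testing". The blow is repeated 15 minutes after salbutamol. A change in FEV1 of at least 12% "will be taken as demonstrating reversible airway narrowing and this in conjunction with the clinical history will be taken as diagnostic" of asthma.

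Section 4 summarises the draft algorithm that the study sets out to implement: "where obstructive spirometry is present bronchodilator reversibility should be considered". FeNO, by contrast, "should be considered where spirometry is normal and where obstructive spirometry does not reverse with bronchodilators". The diagnostic criteria in the same section list obstructive spirometry and "Reversibility following short acting beta-2-agonists" as two objective tests, the second defined as an FEV1 increase of at least 12%. Raised FeNO and peak flow variability are also listed. The list closes with "No single positive test is diagnostic for asthma". Obstructive spirometry is given no numerical definition, and the algorithm figure is not available in the text reviewed.

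Two results depend on these rules. Section 5.2, under the impact of the new NICE guidelines, counts "The number of children in which a diagnosis of asthma can be confirmed using spirometry and FeNO testing". Section 9.1 (Capacity Requirements) states: "We will assess additional capacity needs by timing how long each lung function test takes to perform". It then uses those timings and the number of patients per session to inform the cost of the recommended practice.

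**The concern.** The trigger in Section 8.3 is an either/or rule. A child with FEV1 below 80% predicted and a ratio that is not low is tested. If FEV1 then changes by 12% or more and the history fits, that child is taken as having asthma. If obstructive means a low ratio, which is the ordinary reading, the child has one positive objective test, and Section 4 says one is not enough. The history does not supply the second, because Section 4 lists symptoms separately from the objective tests.

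Objective 1 could therefore include children whom the protocol's own summary of the guideline would not confirm on these tests. The capacity result could include reversibility tests that the summary does not call for. Both would be reported under the guideline's name. There is also a smaller mismatch: Section 8.3 speaks of a change, Section 4 of an increase.

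**Working it through.** The documents give no figure to reproduce here: no share of children with low FEV1 and a normal ratio, and no reversibility rate. The check is a comparison of the two rules, followed by an illustration of size.

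**Step 1: who is tested.** Section 4 is read in two ways, because it does not define obstruction.

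| FEV1/FVC ratio | FEV1 % predicted | Section 8.3 | Section 4 if obstructive = low ratio | Section 4 if obstructive = low ratio or FEV1 <80% |
|---|---|---|---|---|
| Low | 80 or more | Tested | Considered | Considered |
| Low | Below 80 | Tested | Considered | Considered |
| Not low | Below 80 | Tested | Not called for | Considered |
| Not low | 80 or more | Not tested | Not called for | Not called for |

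Only the third row differs. Under the first reading, the Section 8.3 group contains the whole Section 4 group plus that row, so the number of tests is equal or higher, never lower. Under the second reading, the entry groups coincide.

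**Step 2: how many positive objective tests a reversible child has.** In rows 1 and 2 there are two: obstruction and reversibility. In row 3 there is one under the first reading (reversibility) and two under the second.

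**Step 3: illustration of size.** Inputs:
- N = 1000 children (Section 11.2). This is a feasibility number: 1500-2000 eligible × 50-70% response = 750-1400, which contains 1000.
- Wait per test = 15 minutes (Section 8.3).
- q = share with FEV1 below 80% and a ratio that is not low. Assumed, 1-10%.
- r = share of those with a change of 12% or more and a compatible history. Assumed, 5-40%.

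Extra tests = N × q. Waiting time = N × q × 15/60 hours. Extra diagnoses = N × q × r.

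| q | Extra tests | Waiting time | Extra diagnoses, r = 5% to 40% |
|---|---|---|---|
| 1% | 10 | 2.5 h | 0.5 to 4 |
| 3% | 30 | 7.5 h | 1.5 to 12 |
| 5% | 50 | 12.5 h | 2.5 to 20 |
| 10% | 100 | 25 h | 5 to 40 |

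The diagnosis column does not subtract children who also have raised FeNO or peak flow variability and so have a second positive test. The number resting on reversibility alone could be lower.

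**Step 4: scale against clinic time.** Section 17 funds 200 review sessions, so 1000/200 = 5 children per session. At q = 5%, 50/200 = 0.25, or one extra test in every four sessions, and 12.5 × 60/200 = 3.75 minutes of waiting per session on average.

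**The case against.** The strongest reply is that Section 8.3 may be the protocol's working definition of obstructive spirometry: a low ratio or FEV1 below 80%. On that reading there is no wider entry rule, no extra workload and no diagnosis on a single test. The missing figure might settle it. This stands as far as it goes: the conflict depends on a definition that is not given. It does not remove the point, because the two sections agree only under a definition that neither states.

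Several stronger readings are tempting but not supported:
- A reader might infer that the guideline tests reversibility only in obstruction. Section 4 says it should be considered where obstruction is present; the word 'only' is not there.
- A reader might infer that the two groups cannot be told apart later because the trigger is not listed as recorded. They can. Sections 8.3 and 15 place the lung function data and traces in the practice record, consent covers access to it, and Section 8.2 records date of birth, gender, race and height. What is missing is a plan to make the split.
- A reader might size the group by assuming FEV1 % predicted is normal with mean 100 and SD 10-14, which puts 2.3-7.7% below 80. That describes children without airway disease and treats every ratio as normal, whereas this cohort is selected on asthma registration, treatment or exacerbation.
- A reader might infer that 'change' lets a fall in FEV1 count. The sentence follows a bronchodilator and refers to reversible narrowing, so this is a wording mismatch, not a likely source of error.

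On workload, the time per test does not depend on how many children qualify, and other review tasks may fill the 15-minute wait. Both points stand. What can be inflated is the number of tests and hence the total time.

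**Conclusion.** The point holds as an inconsistency to be reconciled. Sections 4 and 8.3 differ on when reversibility is tested and on what confirms asthma. If obstructive means a low ratio, a child with a normal ratio can enter the objective 1 count on one positive objective test, and the number of reversibility tests is equal to or above that of the summarised guideline. If obstructive is meant to include FEV1 below 80% alone, the difference disappears.

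It does not follow that the confirmed count and workload are in fact not the guideline's. That depends on the missing definition and on a share the documents do not give. The illustrative range of 10-100 extra tests and about 0.5-40 extra diagnoses per 1000 rests wholly on the assumed q and r, and the true effect may be small. The case for acting is that the results carry the guideline's name and the remedy is cheap.

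**What to change.** 1. Reconcile Sections 4 and 8.3 on the trigger for reversibility, on what confirms asthma, and on 'change' versus 'increase'. Which rule applies is for the clinical team.
2. State what obstructive spirometry means for the analysis, in terms of ratio, FEV1 or both.
3. Derive the trigger for each child from the stored FEV1 and FVC, or record it on the CRF: low ratio, or FEV1 below 80% with a normal ratio.
4. Report objective 1, and the number and time of reversibility tests, separately for those two routes. The results can then be read under either definition.

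The cost is one derived variable and one split row in the results. Section 8.8 names only spirometry and FeNO times as CRF source data, so a separate time entry is needed if reversibility is not already timed on its own. The downside is that the number of children meeting the Section 4 criteria may be lower than the pooled count.

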8.4 Randomisation and Codebreaking

There is no randomisation of participants in this study.

8.5 Subsequent Assessments

We will have only one face to face contact with each study participant throughout the study. Having taken appropriate consent, we will review each participants electronic record 3-6 months following the initial asthma review to record any changes in prescription patterns, additional primary care review for exacerbations or hospital attendances. In patients who have agreed, we will also send out a follow up postal health economic questionnaire and asthma control test 3-6 months following the review.

8.6 Definition of End of Trial

The end of trial is when the last participant has attended his/her asthma review clinic and we have reviewed his/her records 3-6 months following this date.

8.7 Discontinuation/Withdrawal of Participants from Study Treatment

Each participant has the right to withdraw from the study at any time and may withdraw consent for their patient records to be accessed by informing the study team directly or via their GP.

8.8 Source Data

Source documents are original documents, data, and records from which participants' CRF data are obtained. These include, but are not limited to, GP electronic records (from which medical history and previous and concurrent medication may be summarised into the CRF) and hospital correspondence.

CRF entries will be considered source data if the CRF is the site of the original

recording (e.g., there is no other written or electronic record of data). In this study the CRF will be used as the source document for time taken to perform spirometry and FeNO and health economic questionnaire answers only.

All documents will be stored safely in confidential conditions. On all study-specific documents, other than the signed consent, the participant will be referred to by the study participant number/code, not by name.

9. TREATMENT OF TRIAL PARTICIPANTS

9.1 Description of Study Treatment

Educational sessions for Primary Care Staff

We will provide 2 levels of education:

Level 1: This will be conducted by the implementation team as part of the initial meeting with the GPs, PN/HCAs and managers/administrators. These will be update sessions on the latest draft asthma guidelines issued by NICE and BTS/SIGN with an emphasis on proposed changes to current practice. We will discuss in more detail the diagnostic algorithm for children under investigation for asthma and the objective tests underpinning a diagnosis of asthma in children. An understanding of objective tests includes (i) an appreciation that tests need to be technically acceptable to be useful, and (ii) reference values appropriate for the individual are essential for correct interpretation. Equipment needs (incentive spirometry) and NIOX MINO or VERO for FeNO testing will be discussed, as will the training package to be offered by the implementation team.

Level 2: The implementation team will provide formal face-to-face teaching and additional online training material to practice health care workers on performing spirometry and FeNO. In order to maximise the impact of the asthma reviews the initial training intervention will need to be focused, but flexible to the differing learning requirements of the health care professionals involved.

The training session will address practical aspects and clinical interpretation of spirometry in children. We plan to work in small teaching groups (possibly as few as 1-2 people) which will itself lead to mixed teaching methods, including a short PowerPoint presentation (delivered on a laptop), videoclips, demonstrations, opportunities for practical experience with others acting as the subject, and interpretation of results from an available bank of anonymised data/traces.

The training session will cover: **a)** essential physiological principles underlying spirometry **b)** Setting up and calibrating spirometers (directed towards the type of spirometer to be used in that particular practice setting) **c)** how to encourage children of different ages to perform spirometry, including the use of incentive spirometry **d)** how to recognise when sufficient technically acceptable data have been collected for reporting (or when the child is not capable of performing spirometry) and **e)** interpretation of data.

Participants will be shown how to interpret the data first by examining the graphical recordings, ('pattern recognition'), and then by comparing measured outputs (FEV1, FVC, and FEV1/FVC) with predicted values appropriate for the sex, age and height of the child. This approach aims to identify any individual who may have a condition other than asthma (e.g. fixed obstruction), and then quantify the extent of any deficit in lung function. Where measurements are available before and after a bronchodilator the extent of any change in lung function is a measure of bronchial responsiveness.

In addition to training in spirometry, participants will be trained in the performance and interpretation of exhaled nitric oxide testing in children. While this requires careful instructions to be provided to the child so that s/he exhales steadily into the machine, there is minimal requirement for training in interpretation, since this is a straightforward single-number output.

We will also discuss asthma control tests, asthma action plans and inhaler technique but we are aware that many PN/HCAs will be familiar with asthma action plans and the checking of inhaler technique already. PN/HCAs will be able to retain copies of the teaching materials for private learning or revision, and are encouraged to contact the implementation team at any time if they have questions or want further training.

We will supervise the PN/HCAs performing at least 10 paediatric lung function tests or until they are assessed as competent by both the study team and themselves. This will be continually assessed and feed-back given to the PN/HCA. This approach has been employed successfully by the Respiratory Specialist Nurse Team for the Leicestershire Partnership NHS Trust. We will also point nurses towards accredited courses for further training.

A virtually-delivered quality improvement programme designed to improve primary care management for children with asthma has shown increased spirometry quality and improved assessment of asthma severity levels (14).

Success of the intervention will be defined as every participating surgery having a team which can regularly and competently provide objective lung function tests to children 5-16 years old.

Capacity Requirements

We will assess additional capacity needs by timing how long each lung function test takes to perform in addition to the routine asthma review at each surgery. We will also be able to evaluate the number of patients who can be reliably reviewed and tested per session, thus elucidating how many sessions a typical GP practice would have to support in order to provide regular lung function testing to children. This information would further inform the costs required to sustain new NICE recommended practice.

Health Economic Analysis

This will take the form of a questionnaire delivered to parents at the time of the asthma review and a further postal questionnaire 3-6 months following the review. Analysis of this data will be supported by a health economist.

Assessment of Impact of Implementation to Processes of Care

Following the initial review appointment, we will access the electronic records of consented participants. We will seek information on changes to prescribed asthma medications (bronchodilators, oral steroids and inhaled steroids), exacerbations since review, hospital admissions/attendances since review and whether their originally diagnoses had changed as a result of the availability of objective tests.

With parental consent, we will also send out a repeat ACT by post 3-6 months following the initial review.

